Ruminococcaceae. In our published experience, a single enema from a rationallyderived donor was associated with significantly lower total and HE-related hospitalizations compared to patients who were randomized to standard of care, with a stable long-term course over >1 year¹⁰. Our data show that FMT was associated with favorable changes in fecal bile acid (BA) profile with a decrease in proportions of fecal secondary BAs, conjugated BAs and increase in sulfated BAs, indicating a healthier milieu. We also have preliminary data defining the safety of oral FMT capsules in patients with cirrhosis and HE in a current trial led by us¹¹. The use of combined oral *and rectal routes of FMT, which can potentially alleviate both small bowel and colonic translocation are likely to be better than either alone*.

Details of the team's experience with FMT in cirrhosis using enema¹⁰:

In the trial conducted by us under IND 16452, we have recruited 20 subjects with cirrhosis and recurrent HE (the same population proposed for this trial). All subjects completed the 5-month follow-up without SAEs that were associated with FMT. The baseline subject characteristics are:

	No-FMT group	FMT group	P value
	(n=10)	(n=10)	
Age	62.9±9.8	64.5±5.1	0.65
Gender (Men/Women)	10/0	10/0	1.0
Race (Caucasian, African- American, Hispanic, others)	6/3/1/0	7/2/1/0	0.9
MELD score	13.2±3.7	12.0±2.9	0.36

None of the subjects reached a grade of 3 or change in >2 of any of their GI symptoms throughout the study. Similarly, none of the subjects developed clinically relevant hepatic encephalopathy or significant changes in liver chemistries or labs (WBC

>12,000 or <1000/ml, MELD >8 increase, AST/ALT/ALK>10 times ULN). As shown in the table below, there was a significant improvement (reduction in the MELD score) in the FMT group compared to the no-FMT group at day 1 post-FMT (day 6) and day 30 post-FMT (day 35) compared to baseline. No changes in the WBC count were observed.

	No-FMT group	FMT group	P value
	(n=10)	(n=10)	
MELD score			
Day 0 minus day 6	0.6±1.4	-1.5±1.4	0.004
Day 0 minus day 12	0.4±1.3	-0.2±1.3	0.3
Day 0 minus day 35	1.2±2.4	-0.9±1.7	0.04
Serum WBC count			
Day 0 minus day 6	-0.1±0.6	0.1±1.2	0.60
Day 0 minus day 12	-0.53±0.9	0.2±1.0	0.10
Day 0 minus day 35	0.22±0.5	0.2±0.9	0.95

There was a significant reduction in hospitalizations and improvement in brain function in patients randomized to FMT+ antibiotics compared to those randomized to SOC¹⁰.

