Sample size: Based on the published study with rectal FMT¹⁰, we found that standard of care patients had an 80% chance of hospitalization at 6 months, while FMT had a 20% hospitalization rate. Given that we had used antibiotics for this study, we will assume that rectal FMT alone will have a 30% chance of hospitalization rate without antibiotics. We will also assume that oral FMT alone will have a similar hospitalization rate, and their combination will have a 10% hospitalization rate. Using a significance level of α =0.05, a sample size of 25 per group will provide a power of 100% between groups, 20 per group will give a power of 98% to define differences between the groups, while a sample size of 15 patients per group will give a power of 94% between the groups. Therefore, we will enroll 100 patients (25 in each group) for this trial. This sample size calculation will also be valid when we include the second oral FMT with a sample of 10 per group giving 88% power, 15 per group giving 97% power and 25 giving 99% power.

Specialized analyses:

Inflammatory milieu: We will perform the analysis for endotoxemia using the validated Limulus amebocyte lysate (LAL) assay and serum inflammatory cytokines (IL-6, TNF, IL-1b) using ELISA at [name] and [name]'s laboratory at the McGuire VAMC or at Assaygate¹⁴.

Microbial Analysis: Bacterial community composition in stool will be characterized using OTU counts generated as described above. OTU counts will be converted to measures of relative abundance to account for variation in sequencing coverage between samples and compared to the donor sequence. Statistical analysis will be carried out using the statistical software package R. Alpha (α) diversity (richness and evenness of taxa within a population) will be reported using the Shannon Index¹⁵ and Chao1 richness estimator¹⁶. Changes in abundance of individual taxa will also be analyzed using traditional univariate statistical methods. We will use LEfSe (Linear discriminant analysis Effect Size) to determine the features most likely to explain differences. All comparisons will be performed between treatment arms, to gauge donor engraftment in the three FMT-assigned arms, as well as within groups to compare to their baseline microbial composition¹⁷. These will be performed at George Mason University and University of Minnesota. Functional analysis using bile acids, SCFA and metabolomics will also be performed.

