Brain function: These will be administered at visit 1, visit 4 (one month after the second FMT), and end-of-study by [name] and the coordinator/research assistant. Two validated testing strategies, Psychometric Hepatic Encephalopathy Score (PHES) and EncephalApp Stroop Test, which have norms for the Virginia population will be used¹⁸. The PI and his team are well-published in this field and have been administering these for several years to cirrhotic patients. Both these tests showed benefit in the FMT enema trial published by our group in HE¹⁰. PHES is a recommended battery that defines brain dysfunction in cirrhosis¹⁹. It consists of 5 paper and pencil tests (number connection tests A and B, digit symbol test, line tracing test and serial dotting tests), which form a composite score of standard deviations below an age/education-matched community healthy population. This gives a score ranging between -15 and +4. In addition to this continuous score, covert hepatic encephalopathy can be diagnosed with a score <-4 for our population¹⁸. This test battery takes 15 minutes to complete. EncephalApp Stroop^{18, 20} is a freely available computerized test which consists of an easier "Off" state and a more difficult "On" state. The OffTime+OnTime is the output, which is the time taken to complete 5 correct runs in the Off and On states. The output here can be continuous (seconds in the

OffTime+OnTime) or covert hepatic encephalopathy percentage based on local norms¹⁸. This takes 5-7 minutes to complete.

Quality of Life: This will also be administered at Visit 1, Visit 4, one month after the second FMT, and End-of-Study visit. The Sickness Impact Profile (SIP)²¹ is a validated profile for QOL in cirrhosis that the PI and his team have had several years of published experience²²⁻²⁴. SIP consists of 136 questions that pertain to any issues that patients have experienced in the last 24 hours. It has a composite score, two dimensions (physical and psycho-social) and twelve individual domains that are calculated based on norms. A higher score indicates a worse quality of life. This gives only a continuous score as the output. A copy is shown in the Appendix. [name] and the coordinator/research assistant will perform these.

Endpoints and Plan of Analysis:

Primary Endpoint: FMT-related SAEs including HE recurrence within 6 months

Secondary Endpoints (details below):

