- 1. Safety-related (at 6 months): Liver-related hospitalizations, other serious adverse events (SAE) and adverse events related to interventions.
- 2. Microbiota composition: Stool 16SrRNA sequencing and engraftment of donor into recipients.
- Inflammatory milieu: Endotoxemia (LAL), Systemic inflammatory cytokines (IL-6, TNF, IL-1b using ELISA)
- 4. Bile acid profile and gut-liver mediators expression: Bile acid profile using LC/MS in stool and serum and serum C4 (7α-Hydroxy-4-cholesten-3-one).
- 5. Urinary metabolomics to evaluate gut-microbial markers
- 6. Brain function: Two validated testing strategies, PHES and EncephalApp Stroop Test, and Quality of Life: Sickness Impact Profile (a validated profile for healthrelated quality of life in cirrhosis)

Adjudication: Data and safety monitoring for this study will be provided by the Clinical Science Research & Development (CSR&D) centralized Data Monitoring Committee (DMC). The DMC is provided by CSR&D to ensure independent oversight of the safety and integrity of the project. The DMC is an independent multidisciplinary group, whose members have collectively – through research, education, training, experience, and expertise – the requisite knowledge pertinent to the subject areas to be reviewed. Membership details are available on the CSRD website. The DMC will provide an ongoing independent evaluation of this study focused on safety and feasibility, including participant accrual and retention, adverse events monitoring, and data analyses. Meetings will be held three times per year at which recommendations will range from approval to continue (unconditionally or with conditions to be addressed) to probation or possibly termination, if there are problems with enrollment or safety concerns

All outcomes will be compared between groups as well as post-intervention to baseline.

Visits at VCU and VAMC:

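### The sample size is justified only on hospitalisation; no rate, power or precision is given for the primary endpoint (FMT-related SAEs including HE recurrence)

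*Combined protocol and SAP*

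**What the plan says.** All locations are in the combined protocol and SAP.

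- **Sample size.** The starting point is the earlier enema trial: "we found that standard of care patients had an 80% chance of hospitalization at 6 months, while FMT had a 20% hospitalization rate". The planning assumptions follow: "rectal FMT alone will have a 30% chance of hospitalization rate without antibiotics", and "oral FMT alone will have a similar hospitalization rate, and their combination will have a 10% hospitalization rate". "Using a significance level of α =0.05", the paragraph gives power of 100%, 98% and 94% for 25, 20 and 15 per group, and sets enrolment at 100 (25 per group). A second set of figures (88%, 97% and 99% for 10, 15 and 25 per group) is given for the second oral dose, with no new rates.
- **Endpoints and Plan of Analysis.** "Primary Endpoint: FMT-related SAEs including HE recurrence within 6 months". Hospitalisation appears under the first secondary endpoint: "Safety-related (at 6 months): Liver-related hospitalizations, other serious adverse events (SAE) and adverse events related to interventions".
- **Safety and hospitalization analysis.** All-cause unplanned hospitalisation is named as the safety endpoint. The DMC is to decide relatedness for SAEs in FMT-randomised groups.
- **Primary aim (Study Design).** Safety and tolerability, assessed through SAEs and HE recurrence in particular, against placebo. No hypothesis or margin is stated.
- **Earlier enema trial (Rationale).** "All subjects completed the 5-month follow-up without SAEs that were associated with FMT". Ten of its 20 patients received FMT.

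**The concern.** A sample-size justification should tell the reader what the trial can show about its primary endpoint. Here the only calculation concerns another outcome, and it runs in the opposite direction. It assumes that FMT lowers hospitalisation from 80% to between 10% and 30%, whereas FMT-related SAEs are a measure of harm. Power to detect a large benefit on one outcome says nothing about the ability to detect harm on another.

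The protocol says that all outcomes will be compared between groups, so a between-group test of the primary endpoint is foreseeable. If related events are uncommon, that test will probably be non-significant whatever the truth. Beside a stated power of up to 100%, such a result could be taken as evidence of safety that the data do not supply.

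**Working it through.** **1. Reproduce the plan's figures on hospitalisation.** The inputs are 10%, 30%, 30% and 80% from Sample size (80% for placebo, from the standard-of-care rate), α = 0.05, and a four-group chi-square test on 3 degrees of freedom.

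- Mean rate = (0.10 + 0.30 + 0.30 + 0.80)/4 = 0.375.
- Sum of squared deviations = 0.0756 + 0.0056 + 0.0056 + 0.1806 = 0.2675.
- Noncentrality = n × 0.2675/(0.375 × 0.625) = 1.141n, which is 28.5, 22.8 and 17.1 for n = 25, 20 and 15.
- Power = 99.7%, 98.8% and 94.9%, against the stated 100%, 98% and 94%.

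A two-group comparison of 80% v 20% fits about as well (99.8%, 98.9%, 95.1%). The stated figures are therefore sound as figures for hospitalisation.

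**2. Look for the same inputs for the primary endpoint.** The documents give no expected rate, margin, hypothesis, power or precision for FMT-related SAEs or for HE recurrence. Every rate below is an assumption.

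**3. Narrow reading: only FMT-related events count, and placebo is 0%.** A placebo rate near zero is plausible because the DMC relatedness decision is required only for FMT-randomised groups. The test is two-sided Fisher, which the Statistical analysis paragraph names for categorical outcomes.

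- One FMT arm v placebo: 5/25 v 0/25 gives p = 0.0502 and 6/25 v 0/25 gives p = 0.022, so at least 6 events (24%) are needed.
- All FMT v placebo: 11/75 v 0/25 gives p = 0.061 and 12/75 v 0/25 gives p = 0.034, so at least 12 events (16%) are needed.
- With no placebo events, power = P(Bin(25, p) ≥ 6) or P(Bin(75, p) ≥ 12).

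| Assumed FMT rate (placebo 0%) | 25 v 25 | 75 v 25 |
|---|---|---|
| 5% | 0.1% | <0.1% |
| 10% | 3% | 7% |
| 15% | 16% | 45% |
| 20% | 38% | 84% |
| 30% | 81% | >99% |

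**4. Broad reading: any HE recurrence counts, and FMT lowers it.** Two-sided Fisher power by full enumeration:

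| Assumed placebo v FMT rate | 25 placebo v 25 FMT | 25 placebo v 75 FMT |
|---|---|---|
| 20% v 10% | 9% | 22% |
| 30% v 10% | 30% | 58% |
| 50% v 20% | 51% | 77% |
| 50% v 10% | 83% | 98% |
| 80% v 30% | 95% | 99% |

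**5. Precision if no event is seen.** The exact two-sided 95% upper limit is 1 − 0.025^(1/n):

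- one arm, n = 25: 13.7%
- one route (Groups 1 and 2 for oral, 1 and 3 for rectal), n = 50: 7.1%
- all FMT, n = 75: 4.8%

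**The case against.** **Hospitalisation overlaps with the primary endpoint.** Under Stop-points or reportable adverse events, any hospitalisation in the FMT group is an SAE, and another section calls all-cause hospitalisation the safety endpoint. The overlap is real. It also means that hospitalisation should not be labelled an efficacy outcome, because the document treats it as safety in both places. But under the primary endpoint as worded, a hospitalisation counts only if it is FMT-related or is an HE recurrence. Power for a fall in all hospitalisations does not carry over.

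**A reader might infer that power for the primary endpoint is close to zero.** The documents do not support that as a flat statement. It needs three assumptions: only FMT-related events count, placebo is 0%, and the FMT rate is about 10% or less. At 20% v 0% the pooled comparison has 84% power. The endpoint also names HE recurrence, and the Rationale says that HE keeps recurring in a subset of patients despite both standard treatments, so such events need not be rare.

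**A reader might also infer that 0 related SAEs in 20 FMT recipients have been observed.** The enema trial supports 0 in 10, with an upper 95% limit of 30.8%. The capsule trial is reported only as showing no safety signal compared with placebo in 10 FMT patients, which is not a count of zero.

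**The paragraph never claims power for the primary endpoint, and nothing says that a null test will be read as safety.** Both are true. The paragraph names hospitalisation openly and its arithmetic reproduces. The fault is a mismatch between endpoint and sample size, not a miscalculation. The gap remains, because this is the only justification given for enrolling 100 patients.

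**Conclusion.** The concern holds as a mismatch between the sample-size calculation and the primary endpoint. The 94–100% figures describe hospitalisation, and nothing in the documents says what 25 per group can show about FMT-related SAEs including HE recurrence. This part rests on the text alone.

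The size of the shortfall cannot be fixed from the documents. Under the narrow reading with no placebo events, power for one FMT arm v placebo is about 3% or less at related-event rates up to 10%, and 16% to 38% at rates of 15% to 20%. Pooling the FMT arms gives 7% or less and 45% to 84% over the same ranges. Under the broad reading, 25 v 25 power runs from 9% to 95% over the rates tried. Which reading applies is itself undefined, since the endpoint does not say whether an HE recurrence must be FMT-related to count.

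Because the aim is safety and no hypothesis is stated, precision describes the trial's capacity better than power. Even a clean result in one arm (0/25) would leave true rates up to 13.7% within the 95% interval.

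**What to change.** 1. In Sample size, state that the 94–100% figures apply to hospitalisation only and not to the primary endpoint.
2. In Endpoints and Plan of Analysis, state whether HE recurrence counts regardless of relatedness. This comes first, because the meaning of the other figures depends on it.
3. Analyse the primary endpoint by estimation: exact 95% confidence intervals per arm, and a pooled FMT v placebo risk difference with its interval. State the precision in advance. With zero events the two-sided 95% upper limit is 13.7% (n = 25), 7.1% (n = 50) and 4.8% (n = 75). If any HE recurrence counts, zero events are less likely, so also give interval widths at the assumed recurrence rates.
4. State that a non-significant between-group test of the primary endpoint will not be read as showing safety.

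The cost is protocol wording, with no extra patients. The downside is that the stated power looks less favourable for the primary question.

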Aerobes	Fresh	2.53E+05	1.76E+05
	1 freeze-thaw	4.30E+05	4.43E+05
Anaerobes	Fresh	5.80E+07	3.96E+07
	1 freeze-thaw	6.20E+07	5.29E+06

CFUs per mL of Capsules G3 Microbial Emulsion Matrix

_CFUs per mL of stool homogenized 1:1 (w/v) with buffer containing 12.5% glycerol and 0.9% saline, after one freeze-thaw cycle

	per mL
Aerobes	4.53E+06
Anaerobes	1.47E+09
Spores	2.00E+06

These concentrations will be used for the upcoming trial to ensure that the material concentrations in our older trials are expanded.

- We anticipate providing 5 capsules at a time for the oral FMT and 60ml of the FMT enema.
- The placebo for the oral FMT will be made using identical capsules as the active drug, except it will contain 10%/weight trehalose (the cryoprotectant used in preparation of freeze-dried microbiota) and the rest carboxymethylcellulose. Since the capsules are not transparent and have no specific smell or taste, there should be no difficulty in maintaining double blinding.
- The placebo for the liquid formulation is non-bacteriostatic, sterile phosphate buffered saline containing 10% USP grade glycerol. Each dose will be packaged in individual cryobags, just as the active drug.

Study Design

Overall objective: To determine the effect of dual oral and rectal administration of FMT from a rational donor on clinical outcomes (hospitalizations, brain function, quality of life) and host-microbiota interactions (microbial composition and bile acid composition with systemic and intestinal inflammation), compared to single route of administration and placebo, along with a second oral capsular FMT vs placebo administration in patients with cirrhosis and HE using a randomized, phase II clinical trial.

Design overview:

Four groups of outpatients with cirrhosis will be randomized using random sequence generator into placebo and FMT groups and followed for 6 months under an FDA IND double-blind clinical trial.

Group 1: Dual oral and rectal FMT, Group 2: Oral FMT and rectal placebo, Group 3: Oral placebo and rectal FMT and Group 4: Oral and rectal placebo

A repeat oral capsular FMT vs placebo based on the group assignments above will be provided to every subject in at day 30.

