Dosage: FMT Procedure #1 5 FMT capsules or 5 placebo capsules and 60 ml FMT enema vs 60 ml placebo FMT Procedure #2 5 FMT capsules or 5 placebo capsules

Route of Administration: Oral and enema for baseline, and oral only for Day 30

Timing of administration: Twice (at baseline and Day 30)

Procedures:

Once patients are randomized 1:1:1:1 into Group 1: Dual oral and rectal FMT, Group 2: Oral FMT and rectal placebo, Group 3: Oral placebo and Rectal FMT and Group 4: Oral and rectal placebo, both will be followed over 6 months with intensive follow-up in the first 30 days.

At the end of one month, we will provide another oral-route FMT or placebo to all subjects based on their initial assignment (Groups 1 and 2 will get oral FMT 5 capsules again, and Groups 3 and 4 will get 5 capsules of placebo again). All subjects will be followed with monthly visits till 6 months to assess SAEs.

An overview is shown below in Figure 1 (extended through 6 months)

Procedures:

Visit 1: After initial review of the medical record is completed and informed consent is obtained, potentially eligible patients will be interviewed and their questions about the study will be answered by the study team. Vital signs (including heart rate, blood pressure, respiratory rate, temperature) and weight will be measured. Physical exam will be performed. We will administer the Mini-mental status exam (MMSE)^{13 4}. For those <25, we will deem them not able to give consent and their clinicians will be notified. For the rest we will obtain blood and urine for further confirming eligibility (MELD score and complete blood count for platelet count/ANC). Patients will also be administered a safety test capsule orally to ensure they can swallow it without any issues. If the subject is eligible and can swallow the capsules and otherwise fits criteria, they will be randomized into one of the four groups (Groups 1-4, Table 2) and a date for visit 2 will be generated. A dietary recall will be performed and the patients will be asked to stay on the same diet throughout the trial. We will perform the validated lactulose/mannitol testing at baseline. Patients will undergo brain function tests and quality of life assessment during this visit to establish their baseline. Patients will be given a Stool Collection Kit to bring in the day of the baseline visit (Visit 2). They will also be given a symptom diary and instructions to complete it.

Table 2: Patient Groups

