3. The following will be recorded in all interventions (dose, Unit ID/Lot# of each treatment, Expiration Date and storage condition)

Number of interventions: One administration of rectal placebo or FMT and two administrations of oral FMT or placebo

We will ensure that each subject receiving active FMT will receive material (oral/rectal) from the same donor.

Duration of Follow-up after FMT: 6 months

Samples collected at baseline (before FMT), and at the visits specified above will be:

- a. Stool (microbiome, bile acid profile, metagenomics, metabolomics)
- Blood (CBC, Basic metabolic panel, LFTs, INR, endotoxin, and storage for circulating microbiome, systemic inflammatory markers, bile acids and metabolomics)
- c. Urine for metabolomics

Sample processing will be done using standard precautions at the McGuire VA Medical Center and samples will be stored for analysis of the secondary endpoints. Microbiota analysis will be performed at George Mason University and University of Minnesota, and metabolomics will be performed at the UC Davis NIH West Coast Metabolomics Center or Metabolon. We will perform the bile acid analysis at the McGuire VA Medical Center laboratories. Additional analyses at the Institute of Hepatology, London, UK, and the University of North Carolina at Chapel Hill. We may also use other referral laboratories as needed.

Statistical analysis: These will be performed using ANOVA of delta changes after intervention/follow-up using Chi-square and Fisher exact for non-parametric (hospitalizations, HE episodes, covert hepatic encephalopathy etc.), for continuous variables, and specialized bio-informatics analyses for the microbiota (see details below). These will be adjusted for age, gender, MELD score and alcoholic etiology of cirrhosis.

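### The sample-size section gives one power figure for differences between groups, but on its own rates dual versus single-route FMT has only about 31–45% power at 25 per group

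*Combined protocol and SAP*

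**What the plan says.** All planning figures are in the Sample size section. From the earlier enema trial it takes 80% hospitalization at 6 months under standard of care and 20% with FMT. For this trial it raises the rectal-only rate to 30% because no antibiotics are given, assumes about the same for oral only, and adds that "their combination will have a 10% hospitalization rate". At a significance level of 0.05 it says that "a sample size of 25 per group will provide a power of 100% between groups", with 98% at 20 per group and 94% at 15. It names no test, sidedness, pair of groups or multiplicity rule. A further sentence declares the calculation valid when the second oral dose is included, "with a sample of 10 per group giving 88% power, 15 per group giving 97% power and 25 giving 99% power".

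Four other places bear on how these figures should be read:

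- The overall objective (Study Design) is to assess dual FMT on clinical outcomes, including hospitalizations, "compared to single route of administration and placebo".
- The Statistical analysis paragraph analyses event outcomes "using Chi-square and Fisher exact for non-parametric (hospitalizations, HE episodes" and others, with adjustment for four covariates.
- Endpoints and Plan of Analysis gives "Primary Endpoint: FMT-related SAEs including HE recurrence within 6 months", and later states: "All outcomes will be compared between groups as well as post-intervention to baseline".
- The Procedures text under Intervention fixes the day-30 dose by original assignment: "Groups 1 and 2 will get oral FMT 5 capsules again, and Groups 3 and 4 will get 5 capsules of placebo again".

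**The concern.** A separate 10% rate for the combination, followed directly by a power for differences between the groups, invites the reader to apply that power to every comparison, including dual against single route. That comparison tests whether two routes are better than one, and the overall objective names it. It is also the smallest difference that the planning rates imply (20 points, against 50 and 70 points for the comparisons with placebo).

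If its power is far below the stated figure, a non-significant result could be read against a nominal 100% power as evidence that the second route adds nothing. It would in fact be the likelier outcome even if the plan's assumptions were exactly right.

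**Working it through.** **Inputs (Sample size section).** Rates: placebo 0.80, each single route 0.30, dual 0.10; earlier-trial FMT rate 0.20. Alpha 0.05. 25 per group, allocated 1:1:1:1 (Procedures). Sidedness and dropout are not stated; I assume two-sided and none. The tests are those named for hospitalizations, Pearson chi-square and Fisher exact, both unadjusted. Two-group powers are exact: sum Bin(x; n, p1) × Bin(y; n, p2) over all tables (x, y) with p ≤ 0.05.

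**Step 1: reproduce 94/98/100%.** Two routes come close.

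(a) 80% versus 20%, Pearson: 94.1/98.2/99.7% at 15/20/25.

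(b) Four-group chi-square on 3 df at 80/30/30/10%. The mean rate is (0.8 + 0.3 + 0.3 + 0.1)/4 = 0.375. The squared deviations sum to 0.1806 + 0.0056 + 0.0056 + 0.0756 = 0.2675. The noncentrality is n × 0.2675/(0.375 × 0.625) = 1.141n, that is 17.1, 22.8 and 28.5. Power by noncentral chi-square is 94.9/98.8/99.7%. Simulation of the same test gives 97.5/99.7/99.95%, so this match depends on the approximation.

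Both results come mainly from the 80% rate. The same omnibus test on the three FMT arms alone (30/30/10%) has 39% power at 25 per group (40% by simulation).

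**Step 2: power by pair, two-sided 0.05.**

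| Comparison | Test | n=15 | n=20 | n=25 |
|---|---|---|---|---|
| Dual 10% vs single 30% | Fisher | 14.9% | 24.2% | 30.5% |
| | Pearson | 27.8% | 35.7% | 45.0% |
| Single 30% vs placebo 80% | Fisher | 68.0% | 84.6% | 94.6% |
| | Pearson | 81.5% | 90.8% | 97.2% |
| Dual 10% vs placebo 80% | Fisher | 97.5% | 99.7% | 99.98% |
| | Pearson | 99.2% | 99.9% | 100% |

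Hand check of the first pair at n = 25 by the pooled normal formula: Φ[(0.20 − 1.96√(2 × 0.2 × 0.8/25)) / √((0.21 + 0.09)/25)] = Φ[(0.20 − 0.2217)/0.1095] = Φ(−0.199) = 42.1%, which lies inside the range.

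**Step 3: more favourable readings of dual versus single.**

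- One-sided 0.05 Pearson, 25 per group: 57.2%.
- Dual (25) against both single-route arms pooled (50), two-sided: 45.3% (Fisher) to 51.9% (Pearson).
- Pooled and one-sided Pearson: 65.8%.

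None approaches 100%. A multiplicity adjustment would lower all of them.

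**Step 4: what 25 per group can deliver.** The smallest n per group for 80% power at 30% versus 10% is 59 (Pearson, 80.5%) or 69 (Fisher, 80.7%). The 95% CI half-width at n = 25 is 1.96 × √(0.3 × 0.7/25 + 0.1 × 0.9/25) = 1.96 × 0.1095 = 0.215, or 21.5 points around an assumed difference of 20.

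**Step 5: the second-FMT series.** The 88/97/99% at 10/15/25 cannot be checked, because no rates and no contrast are given. The series is 3 points above the first at 15 per group and 1 point below it at 25, without explanation. Because every participant repeats the original oral assignment, no randomised comparison separates the second dose from the first.

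**Step 6: the endpoint.** The calculation is for hospitalization, which the Safety and hospitalization analysis section treats as a safety endpoint. The primary endpoint is FMT-related SAEs including HE recurrence. No rate is assumed for it.

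**The case against.** The best defence is that nothing is miscalculated: 94/98/100% can be reproduced to within 2 points, and the text never claims that power for each pair. On this view it describes an overall test, the primary aim is safety, most of the numbered aims compare with placebo or baseline, and no passage makes dual versus single route a confirmatory test.

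Much of this is fair. The fault is an incomplete power statement, not a wrong sum. The defence does not remove it, for three reasons. The text does not say that an overall test was meant. A significant overall test at these rates would mainly reflect the placebo arm and would not show that dual FMT is better than one route. And the overall objective and the analysis plan both include the comparison.

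Some qualifications stand. The closest match, 80% versus 20%, is not a contrast between any two arms of this trial, since no arm is assumed to have a 20% rate. The pairwise powers above are unadjusted, whereas the plan adjusts for age, gender, MELD score and alcoholic etiology; adjustment is unlikely to close so large a gap. The second-FMT sentence does not claim to isolate the second dose, so the complaint there is mainly the missing rates and contrast. Hospitalizations generally count as SAEs in this protocol, so the powered outcome overlaps with the primary endpoint, but the latter is limited to FMT-related events.

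**Conclusion.** The concern holds. The power statement names no test or contrast, and its figures cannot describe dual versus single-route FMT. On the plan's own rates that comparison has 30.5% (Fisher) to 45.0% (chi-square) power at 25 per group, and no more than about 66% on the most favourable reading tried. A two-sided test against one single-route arm would therefore miss the assumed 20-point difference 55–69% of the time. These figures assume two-sided 5%, no dropout, no multiplicity correction and unadjusted tests.

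The comparisons with placebo are adequately powered at 25 per group, although single route versus placebo falls below the stated series at 15 and 20. The second-FMT figures have no stated basis, and the primary endpoint has no power or precision statement.

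**What to change.** Keep 100 patients and rewrite the Sample size paragraph as follows.

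1. Name the test, sidedness and contrast behind 94/98/100%.
2. Give power by comparison at 25 per group (two-sided 0.05, unadjusted): four-group test above 99%; each single route versus placebo 95–97%; dual versus placebo about 100%; dual versus either single route 31% (Fisher) to 45% (chi-square).
3. State that dual versus single route will be reported as a risk difference with a 95% confidence interval (expected half-width about 21 points), not as a powered test.
4. Delete the second-FMT power sentence, or give its rates and the contrast it refers to.
5. State that the calculation is for 6-month hospitalization and not for the primary endpoint of FMT-related SAEs including HE recurrence.

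This costs wording only, with no added patients or procedures. The price is a much less favourable stated power for dual versus single route, which becomes a matter of estimation. Powering it at 80% would instead need 59 to 69 per group, more than twice the planned size.
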